9.2. Efficacy Endpoints

9.2.1. Primary Efficacy Endpoint

Time from randomization to the first occurrence of the composite of the following clinical events:

- CV death,
- Nonfatal MI (including silent MI; ECGs will be performed annually for the detection of silent MIs),
- Nonfatal stroke,
- Coronary revascularization
- Hospitalization for unstable angina determined to be caused by myocardial ischemia by invasive/non-invasive testing.

The first occurrence of any of these major adverse vascular events during the follow-up period of the study will be included in the incidence.

9.2.2. Secondary Efficacy Endpoints

The key secondary efficacy endpoint is:

- The composite of death from CV causes, nonfatal MI, coronary revascularization, unstable angina determined to be caused by myocardial ischemia by invasive/non-invasive testing and requiring emergent hospitalization, nonfatal stroke, or peripheral CVD requiring intervention, angioplasty, bypass surgery, or aneurysm repair.

Other secondary efficacy endpoints are as follows (to be tested in said order):

- The composite of total mortality, nonfatal MI, or nonfatal stroke;
- The composite of death from CV causes, nonfatal MI, coronary revascularization, unstable angina determined to be caused by myocardial ischemia by invasive/non-invasive testing and requiring emergent hospitalization, peripheral CVD requiring intervention, or cardiac arrhythmia requiring hospitalization;
- The composite of death from CV causes, nonfatal MI, coronary revascularization, or unstable angina determined to be caused by myocardial ischemia by invasive/non-invasive testing and requiring emergent hospitalization;
- The composite of death from CV causes or nonfatal MI;
- Total mortality;
- Fatal and nonfatal MI (including silent MI);
- Coronary Revascularization;
- Hospitalization for unstable angina determined to be caused by myocardial ischemia by invasive/non-invasive testing ;
- Fatal and nonfatal stroke.

For the secondary endpoints that count a single event, the first occurrence of this type of event will be counted in each patient. For secondary endpoints that are composites of two or more types of events, the first occurrence of any of the event types included in the composite will be counted in each patient.

9.2.3. Tertiary Efficacy Endpoints:

- The second, third, fourth, and fifth major CV event of the primary composite endpoint. The type of (nonfatal) events may occur in any order.
- Primary endpoint in subset of patients with diabetes mellitus;
- Primary endpoint in subset of patients with metabolic syndrome;
- New CHF, new CHF leading to hospitalization, transient ischemic attack, amputation for CVD and carotid revascularization;
- Elective coronary revascularization and emergent coronary revascularization;
- New onset diabetes;
- Fasting TG, TC, LDL-C, HDL-C, non-HDL-C, VLDL-C, apo B, hs-CRP, and hsTnT: effect of baseline and on-treatment change of biomarkers on primary and key secondary endpoints;

- CV mortality;
- Cardiac Arrhythmias requiring hospitalization;
- Cardiac Arrest;
- To explore the effect of AMR101 on weight and waist circumference.

For the tertiary endpoints that count a single event, the first occurrence of this type of event will be counted in each patient. For tertiary endpoints that are composites of two or more types of events, the first occurrence of any of the event types included in the composite will be counted in each patient (except when stated otherwise, for the second, third, fourth, and fifth major CV event).

10. SAFETY ASSESSMENTS

10.1. Specification of Variables and Procedures

Safety assessments will include adverse events, clinical laboratory measurements (chemistry, hematology), 12-lead ECGs, vital signs (systolic and diastolic blood pressure, heart rate, respiratory rate, and body temperature), and physical examinations as per Study Procedures/Appendix A.

A complete medical, surgical and family history will be completed at Visit 1.

A list of the analytes to be measured for the safety evaluation is found in Section 6.3.1.1. All laboratory test results must be evaluated by the investigator as to their clinical significance. Any observations at physical examinations or laboratory values considered by the investigator to be clinically significant should be considered an adverse event.

10.2. Adverse Events

An adverse event is defined as any untoward medical occurrence, which does not necessarily have a causal relationship with the medication under investigation. An adverse event can therefore be any unfavorable and/or unintended sign (including an abnormal laboratory finding), symptom, or disease temporally associated with the use of an investigational medication product, whether or not related to the investigational medication product. All adverse events, including observed or volunteered problems, complaints, or symptoms, are to be recorded on the appropriate CRF. Each adverse event is to be evaluated for duration, intensity, and causal relationship with the study medication or other factors.

Adverse events, which include clinical laboratory test variables, will be monitored from the time of informed consent until study participation is complete. Patients should be instructed to report any adverse event that they experience to the investigator. Beginning with Visit 2, investigators should assess for adverse events at each visit and record the event on the appropriate adverse event CRF.

Wherever possible, a specific disease or syndrome rather than individual associated signs and symptoms should be identified by the investigator and recorded on the CRF. However, if an observed or reported sign or symptom is not considered a component of a specific disease or syndrome by the investigator, it should be recorded as a separate adverse event on the CRF.

Any medical condition that is present when a patient is screened or present at baseline that does not deteriorate should not be reported as an adverse event. However, medical conditions

or signs or symptoms present at baseline and that change in severity or seriousness at any time during the study should be reported as an adverse event.

Clinically significant abnormal laboratory findings or other abnormal assessments that are detected during the study or are present at baseline and significantly worsen will be reported as adverse events or SAEs. The investigator will exercise his or her medical and scientific judgment in deciding whether an abnormal laboratory finding or other abnormal assessment is clinically significant.

The investigator will rate the severity (intensity) of each adverse event as mild, moderate, or severe, and will also categorize each adverse event as to its potential relationship to study drug using the categories of Yes or No.

Severity:

- Mild – An event that is usually transient in nature and generally not interfering with normal activities.
- Moderate – An event that is sufficiently discomforting to interfere with normal activities.
- Severe – An event that is incapacitating with inability to work or do usual activity or inability to work or perform normal daily activity.

Causality Assessment:

The relationship of an adverse event to the administration of the study drug is to be assessed according to the following definitions:

- No (unrelated, not related, no relation) – The time course between the administration of study drug and the occurrence or worsening of the adverse event rules out a causal relationship and another cause (concomitant drugs, therapies, complications, etc.) is suspected.
- Yes – The time course between the administration of study drug and the occurrence or worsening of the adverse event is consistent with a causal relationship and no other cause (concomitant drugs, therapies, complications, etc.) can be identified.

The following factors should also be considered:

- The temporal sequence from study medication administration
- The event should occur after the study medication is given. The length of time from study medication exposure to event should be evaluated in the clinical context of the event.
- Underlying, concomitant, intercurrent diseases
- Each report should be evaluated in the context of the natural history and course of the disease being treated and any other disease the patient may have.
- Concomitant medication
- The other medications the patient is taking or the treatment the patient receives should be examined to determine whether any of them might be recognized to cause the event in question.
- Known response pattern for this class of study medication
- Clinical and/or preclinical data may indicate whether a particular response is likely to be a class effect.

- Exposure to physical and/or mental stresses
- The exposure to stress might induce adverse changes in the patient and provide a logical and better explanation for the event.
- The pharmacology and pharmacokinetics of the study medication
- The known pharmacologic properties (absorption, distribution, metabolism, and excretion) of the study medication should be considered.

Unexpected Adverse Events – An unexpected adverse event is an adverse event either not previously reported or where the nature, seriousness, severity, or outcome is not consistent with the current Investigator’s Brochure.

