Fibrates are clearly effective at raising HDL-C and lowering TG concentrations. However, their effects on vascular events remain uncertain. Several large-scale trials of fibrate therapy have been completed in the past few years. Although some of these trials have suggested benefit, others have shown no effect, leading to uncertainty about the presence and magnitude of any cardiovascular protective effects and difficulties for clinicians in interpretation of the results (Jun 2010). The ACCORD study (Ginsberg 2010) reported no overall benefit for fenofibrate, raising further questions about the usefulness of these agents.

There are also safety issues with the above agents that limit their clinical use. Statins, particularly at high doses, may cause increases in hepatic transaminases and are also known to cause myopathy and occasionally rhabdomyolysis, which may lead to death from acute renal failure. This risk may be increased when fibrates and statins are co-administered and many clinicians will avoid co-prescribing these 2 medications. Fibrates are also associated with interactions with warfarin and hepatic transaminase elevations. The utility of niacin is limited by the occurrence of severe flushing and associated symptoms which can be difficult to manage even with careful dose titration and pre administration of aspirin or other non-steroidal anti-inflammatory drugs. Niacin is also associated with impairment of glucose tolerance and precipitation of attacks of gout in susceptible patients.

The DYSlipidemia International Study (DYSIS) assessed the prevalence of dyslipidemia among patients taking statins. This epidemiological observational study included more than 22,000 patients in Europe and Canada aged 45 and older who received statin therapy for at least three months, and had a clinical diagnosis of coronary or other atherosclerotic disease, or were at high risk of developing CVD. The study found 48% of patients had LDL-C not at goal; 26% had low HDL-C levels; and 38% had elevated triglycerides. This study demonstrates that persistent dyslipidemia is highly prevalent in statin-treated patients.

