4. STUDY POPULATION

4.1. Inclusion Criteria

Patients meeting the following criteria will be eligible to participate in the study:

1. Fasting TG levels of ≥ 200 mg/dL (2.26 mmol/L) and < 500 mg/dL (5.64 mmol/L).
2. LDL-C > 40 mg/dL (1.04 mmol/L) and ≤ 100 mg/dL (2.60 mmol/L) and on stable therapy with a statin (with or without ezetimibe) for at least 4 weeks prior to the LDL-C/TG baseline qualifying measurements for randomization
 - Stable therapy is defined as the same daily dose of the same statin for at least 28 days before the lipid qualification measurements (TG and LDL-C) and, if applicable, the same daily dose of ezetimibe for at least 28 days before the lipid qualification measurements (TG and LDL-C). Patients who have their statin therapy or use of ezetimibe initiated at Visit 1, or have their statin, statin dose and/or ezetimibe dose changed at Visit 1, will need to go through a stabilization period of at least 28 days since initiation/change and have their qualifying lipid measurements measured (TG and LDL-C) after the washout period (at Visit 1.1).
 - Statins may be administered with or without ezetimibe.

NOTE: If patients qualify at the first qualification visit (Visit 1) for TG and LDL-C, and meet all other inclusion/exclusion criteria, they may be randomized at Visit 2. If patients don't qualify at the first qualifying visit (Visit 1), a second re-qualifying visit (Visit 1.1) is allowed. For some patients, because they need to stabilize medications and/or need to washout medications, the second re-qualifying visit (Visit 1.1) will be needed after the stabilization/washout period.

3. Either having established CVD (in CV Risk Category 1) or at high risk for CVD (in CV Risk Category 2). The CV risk categories are defined as follows:

CV Risk Category 1: defined as men and women ≥ 45 years of age with one or more of the following:

- Documented coronary artery disease (CAD; one or more of the following primary criteria must be satisfied):
 - Documented multivessel CAD ($\geq 50\%$ stenosis in at least two major epicardial coronary arteries – with or without antecedent revascularization)
 - Documented prior MI
 - Hospitalization for high-risk NSTEMI-ACS (with objective evidence of ischemia: ST-segment deviation or biomarker positivity)
- Documented cerebrovascular or carotid disease (one of the following primary criteria must be satisfied):
 - Documented prior ischemic stroke

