10.3. Serious Adverse Event Reporting – Procedure for Investigators

10.3.1. Initial Reports

All SAEs occurring from the time of informed consent until 28 days following the last administration of study medication must be reported to the Sponsor or designee **within 24 hours** of the knowledge of the occurrence (this refers to any adverse event that meets any of

the aforementioned serious criteria). SAEs that the investigator considers related to study medication occurring after the 28-day follow-up period will also be reported to the Sponsor or designee.

The investigator is required to submit SAE reports to the Institutional Review Board (IRB) or Independent Ethics Committee (IEC) in accordance with local requirements. All investigators involved in studies using the same investigational medicinal product (IMP) will receive any Suspected Unexpected Serious Adverse Reaction (SUSAR) reports for onward submission to their local IRB as required. All reports sent to investigators will be blinded.

In addition, regulatory agencies will be notified of SAEs per the requirements of the specific regulatory jurisdiction regulations and laws.

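### The Yes/No causality definitions in section 10.2 leave an event with plausible timing and another possible cause in neither category, so ratings will differ between sites and suspected reactions may be under-identified

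*Combined protocol and SAP*

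**What the plan says.** Under Amendment 1, section 10.2 (Adverse Events), the investigator must "categorize each adverse event as to its potential relationship to study drug using the categories of Yes or No". There is no intermediate or unknown category. The Causality Assessment part of that section then defines the two answers:

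- *No*: the time course "rules out a causal relationship and another cause (concomitant drugs, therapies, complications, etc.) is suspected".
- *Yes*: the time course "is consistent with a causal relationship and no other cause (concomitant drugs, therapies, complications, etc.) can be identified".

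A list of further factors follows (timing, underlying disease, other medication, class effects, stress, pharmacology). On other medication it says that these drugs "should be examined to determine whether any of them might be recognized to cause the event in question". The list gives no rule for an event that fits neither definition.

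The rating is used elsewhere. Section 10.3.1 (Initial Reports) requires all SAEs up to 28 days after the last dose to be reported to the sponsor. Beyond that, reporting depends on the rating: "SAEs that the investigator considers related to study medication occurring after the 28-day follow-up period will also be reported to the Sponsor" or its designee. Sections 10.3.1 and 10.3.3 provide for SUSAR reports. Section 7.1.2.3 (Emergency Unblinding) asks for a Yes/No judgment before the code is broken.

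On the population, inclusion criterion 2 (section 4.1) requires patients to be "on stable therapy with a statin (with or without ezetimibe) for at least 4 weeks" before the qualifying lipid measurements. Section 1.5 (Rationale) says that statins "may cause increases in hepatic transaminases and are also known to cause myopathy and occasionally rhabdomyolysis".

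**The concern.** Each definition joins two conditions with *and*, and neither is the negation of the other. An investigator who follows the text has no answer for an event whose timing fits the study drug but which something else might also have caused. In this trial that situation should not be rare: all patients enter on a statin, and all have established cardiovascular disease, or diabetes with a further risk factor.

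The standard for Yes also sits badly with its purpose. The investigator is asked about a potential relationship, and the S in SUSAR stands for suspected. A definition that requires every other cause to be absent is a test by exclusion, which is stricter than suspicion.

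Two things are at stake. Relatedness ratings may not be comparable between sites, because each site must invent its own rule for the undefined case. And a site that applies Yes literally could fail to flag a suspected reaction where the flag decides what happens next: SUSAR identification and SAEs after the 28-day window. That window matters because patients who stop study drug but have not withdrawn consent remain under follow-up until the study ends (sections 11.1 and 11.2).

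**Working it through.** The plan gives no figure on this point, so the check is a truth table followed by a trace of where the rating is used.

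**Step 1: the two definitions against the four possible cases.**

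| Case | Time course | Other cause | Meets Yes? | Meets No? | Category |
|---|---|---|---|---|---|
| 1 | consistent | none identified | yes | no | Yes |
| 2 | consistent | identified | no (second condition fails) | no (first condition fails) | none |
| 3 | ruled out | suspected | no | yes | No |
| 4 | ruled out | none suspected | no | no (second condition fails) | none |

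Two of four cases have no category. Case 4 has an obvious practical answer, since excluded timing points to No. Case 2 has none.

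**Step 2: an example from the protocol's own statements.** A patient on study drug and a statin has a transaminase rise with consistent timing. It is not No, because the timing does not rule out causality. It is not Yes, because section 1.5 names statins as a recognized cause. The additional factors do not settle it; they direct the investigator towards alternatives, and each one found blocks a literal Yes.

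**Step 3: how far a literal Yes could shrink.** Let f be the share of events with consistent timing that also have another identifiable cause. The documents give no value, so f is an assumption. On a strict reading, at most 1 − f of these events can be rated Yes:

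- f = 0.2: 1 − 0.2 = 80%
- f = 0.5: 1 − 0.5 = 50%
- f = 0.8: 1 − 0.8 = 20%
- f = 0.95: 1 − 0.95 = 5%

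The effect ranges from modest to severe, and nothing in the documents places f in that range.

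**Step 4: what depends on the rating.**

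| Output | Depends on Yes/No? | Source |
|---|---|---|
| SAE reports up to 28 days after last dose | No (endpoint events handled separately) | 10.3.1, 10.2.1 |
| SAE reports after 28 days | Yes | 10.3.1 |
| SUSAR identification | Yes, as a suspected reaction | 10.3.1, 10.3.3 |
| Judgment recorded before emergency unblinding | Yes | 7.1.2.3 |
| Overall TEAE incidence | No | 12.2.5 |

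**The case against.** The strongest reply is that the gap is real but little hangs on it. SAEs up to 28 days after the last dose reach the sponsor within 24 hours of becoming known, whatever the rating, endpoint events apart. All adverse events are recorded until a patient's participation ends, including for patients off drug. Section 12.2.5 tabulates overall TEAE incidence without regard to relationship, the DMC reviews safety (section 5.4), and statins are taken in both arms, so the randomized comparison of event rates does not use the investigator's opinion. Section 11.1 also lists certain ALT elevations as reasons to consider discontinuation without reference to causality, and asks that the sponsor be told when a patient is discontinued for a laboratory abnormality. Nothing says that the site's answer is the only input to a SUSAR decision.

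Most of this stands, and it limits the reach of the point. It does not close the gap for SAEs after 28 days, or for the investigator's contribution to SUSAR identification.

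Two stronger readings are tempting, and the documents support neither. A reader might infer that almost no event can be rated Yes because every patient takes a statin. But the text asks whether another drug might be recognized to cause the particular event, and the statin harms named in section 1.5 are to liver enzymes and muscle. The reactions reported for ethyl-EPA in section 1.4 are largely of other kinds: arthralgia, oropharyngeal pain, gastrointestinal and skin events. The inference would need f near 0.9 or above. A reader might also infer that suspected reactions are certain to be under-reported. Case 2 fails No as well as Yes, so the text does not fix the direction, and asking about a potential relationship could push a site towards Yes.

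**Conclusion.** The definitions are not complementary, and this follows from the text alone. An event with consistent timing and another identifiable cause has no category although a Yes or No is mandatory, and Yes is set at a stricter standard than the potential relationship being asked about or the suspicion on which SUSAR reporting rests. Inconsistent ratings between sites are the direct consequence. Under-identification of suspected reactions is a plausible further one, if sites apply Yes literally and default to No.

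The size is two of four logical cases, one of them important in practice. How many events fall there cannot be derived from the documents. Exposed are SUSAR identification, SAE reporting after 28 days and the judgment recorded before unblinding. SAE reporting up to 28 days (endpoint events apart) and the overall TEAE tables are not affected. The wording should be corrected, but this is not a threat to the efficacy analysis or to the main safety comparison.

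The conclusion rests on Amendment 1. The original protocol has the same causality definitions in its section 10.2. The file supplies only the title page of Amendment 2, so whether the wording survived there cannot be confirmed.

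**What to change.** Define one category by a stated threshold and the other as its complement:

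- *Yes*: there is a reasonable possibility that study drug contributed to the event, whether or not another possible cause is also present.
- *No*: all other events.

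Cases 1 and 2 are then judged on whether a contribution is reasonably possible, and cases 3 and 4 fall under No because the timing excludes one. The list of additional factors can stay as guidance for that judgment. The sponsor should first check whether Amendment 2 still carries the present definitions.

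The cost is two sentences in section 10.2, matching CRF completion guidance and a memo to sites. The downside is that more events will be rated related and more cases will need expedited review. If the change is made while the trial is running, ratings before and after it will rest on different definitions, and any summary of related events should say so.
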